## 7. HYPOTHESIS AND OBJECTIVES

### 7.1. Primary objective:

- To describe the baseline clinical characteristics of the population of patients who are long-term responders to axitinib and to identify clinical factors associated with a long-term response to axitinib.

*For the study, “long-term responders to axitinib” has been defined as patients with progression-free survival [PFS] of at least 9 months with the drug, and “patients refractory to axitinib” has been defined as patients with disease progression in the first assessment after the start of treatment [estimated PFS  $\leq$ 3 months]*

To meet the study objective, two groups of patients with extreme response to the drug will be compared: a group of patients with long-term responses to the drug (group of long-term responders to axitinib) compared to a group of patients with disease progression in the first assessment after starting treatment (group of patients refractory to axitinib), in which the association of the following clinical factors will be analysed with the benefit of the treatment;

- Age ( $\leq$ 65 years and  $>$ 65 years)
- Baseline ECOG/PS at the start of treatment for each line (0, 1 and  $\geq$ 2)
- Number of previous treatment lines (1, 2 and  $\geq$ 3)
- Previous nephrectomy (yes and no)
- MSKCC risk group (favourable, intermediate and poor)
- IMDC risk group (favourable, intermediate and poor)
- Change in the MSKCC or the IMDC risk group with respect to the previous line (yes vs no);
- Histology (100% clear cells, main component of clear cells, main component of non-clear cells, 100% non-clear cells).

- Duration of first-line with a TKI ( $\geq 12$  months,  $\leq 6$  months;  $\leq 3$  months)
- Better response with the TKI received in first-line (CR/PR, SD, DP)
- Number of metastatic locations (1, 2 and  $\geq 3$ );
- Site of metastases (CNS metastases [yes vs no]; lymph nodes [yes vs no]; lung [yes vs no]; liver [yes vs no]; bone [yes vs no])
- Baseline LDH levels  $\leq 1.5 \times \text{ULN}$  (yes vs no)
- Baseline Hgb levels  $> \text{LLN}$  (yes vs no)
- Baseline corrected  $\text{Ca}^{++}$  levels  $\leq 10$  mg/dl (yes vs no)
- Baseline neutrophil levels  $\leq \text{ULN}$  (yes vs no)
- Baseline platelet levels  $\leq \text{ULN}$  (yes vs no)
- Neutrophil/lymphocyte ratio  $\leq 3$  (yes vs no)
- Smoking habits (smoker, non-smoker or ex-smoker)

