## 6 VARIABLES IN THE CRF

The following groups of variables will be recorded for this observational study: Demographic data, medical history, first-line treatments, other treatments prior to axitinib, treatment with axitinib, subsequent treatments and the patient's vital status. Details of all the variables recorded in the CRF are given below:

- Demographic data:
  - Date of birth
  - Gender
- Clinical history of renal cell carcinoma
  - Date of first diagnosis
  - Tumour stage at disease diagnosis (I/II/III/IV)
  - Non-systemic treatment
    - Nephrectomy (Yes/No/Unknown).
      - If yes, specify:
        - Date (Date/Unknown)
        - Type (Total/Partial/Unknown)
        - Kidney (Right/Left/Unknown)
      - Radiotherapy (Yes/No/Unknown).
        - If yes, specify:
          - Date (Date/Unknown)
      - Histological type (100% Clear cells/ Primarily clear cells/ Primarily non-clear cells/ 100% Non-clear cells)
        - If 100% Clear cells have not been marked, specify (Sarcomatoid/Chromophobe/ type 1 Papillary/ type 2 Papillary/ Other, specify/Not performed)
    - Diagnosis of advanced disease
      - Date
      - Stage (III/IV)
      - Metastasis site (multi-response question):
        - Lymph nodes
        - CNS
        - Liver
        - Lungs
        - Bone
        - Other, specify
      - Risk criteria before the initiation of the first line
        - Time from initial diagnosis to systemic treatment less than 1 year (Yes/No/Unknown)
        - ECOG/PS (Yes/No/Unknown)
        - LDH >1.5 x ULN (Yes/No/Unknown)
        - Haemoglobin < LLN (Yes/No/Unknown)
        - Corrected calcium >10 mg/dl (Yes/No/Unknown)
        - Presence of 2 or more metastatic sites (Yes/No/Unknown)

- 
- Platelets > ULN (Yes/No/Unknown)
  - Neutrophils > ULN (Yes/No/Unknown)- (current value)
  - Lymphocytes (Yes/No/Unknown)- (value)
  - Smoking habits (Smoker/Non-smoker/Former smoker)
  - First-line treatment
    - Drug
    - Starting dose
    - Duration of treatment
      - Start date
      - End date
      - Reason for treatment withdrawal (DP/Toxicity/Other, specify)
      - Has there been disease progression? (No/Yes, specify date)
      - Best treatment response (CR, PR, SD, DP/Not evaluable).
        - Date of the best response obtained
  - Other treatments prior to axitinib
    - Has the patient received other treatments prior to axitinib? (Yes/No/Unknown)
      - If yes, specify:
        - 2nd-line treatment
          - Drug
          - Starting dose

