          - Reason for starting this treatment (DP in the 1st line treatment/Toxicity in the 1st line treatment/Other, specify)
          - Start date
          - End date
          - Reason for treatment withdrawal (DP/Toxicity/Other, specify)
          - Has there been disease progression? (No/Yes, specify date)
          - Best treatment response (CR, PR, SD, DP/Not evaluable).
            - Date of the best response obtained
        - 3rd-line treatment
          - Drug
          - Starting dose
          - Reason for starting this treatment (DP in the 2nd line treatment/Toxicity in the 2nd line treatment/Other, specify)
          - Start date
          - End date
          - Reason for treatment withdrawal (DP/Toxicity/Other, specify)
          - Has there been disease progression? (No/Yes, specify date)

- 
- Best treatment response (CR, PR, SD, DP/Not evaluable).
    - Date of the best response obtained
  - Treatment with axitinib
    - Treatment line in which it was received.
    - Reason for starting treatment with axitinib (DP in previous treatment line/Toxicity in previous treatment line/Other, specify).
    - Risk criteria at the initiation of treatment with axitinib
      - Time from first diagnosis to systemic treatment less than 1 year (Yes/No/Unknown)
      - ECOG/PS (current status) (Yes/No/Unknown)
      - LDH >1.5 x ULN (Yes/No/Unknown)
      - Haemoglobin < LLN (Yes/No/Unknown)
      - Corrected calcium >10 mg/dl (Yes/No/Unknown)
      - Presence of 2 or more metastatic sites (Yes/No/Unknown)
      - Platelets > ULN (Yes/No/Unknown)
      - Neutrophils > ULN (Yes/No/Unknown) (value)
      - Lymphocytes (Yes/No/Unknown) (value)
      - Smoking habits (Smoker/Non-smoker/Former smoker)
    - Presence of comorbidities
      - Kidney failure (Yes/No)
        - If yes, specify, Creatinine Clearance (Mild, 60-89 ml/min/ Moderate, 30-59 ml/min/ Severe, 15-29 ml/min/ End Stage, <15 ml/min/ Dialysis)
      - Liver failure (Yes/No)
        - If yes, specify, Child Pugh (A/B/C)
      - Cardiovascular (Yes/No)
        - If yes, specify (multi-response question)
          - Decreased LVEF, specify %
          - Heart failure
          - Previous arrhythmia
          - Previous ischaemia
          - Controlled HTN, specify number of antihypertensive agents
          - Other, specify
      - Respiratory disease (Yes/No), specify
      - Other comorbidity (Yes/No), specify
    - Start date of treatment with axitinib

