## 7 DEFINITION OF VARIABLES AND OBJECTIVES

In addition, the following variables will be calculated from the CRF data:

NOTE: In patients with dates after the date of the IC visit / signature, the date of the IC visit / signature has been considered as the date of the last check. Due to the retrospective nature of the study, no data can be collected after the patient was included in the IC study / signature.

- Age (years) of patient at time of visit= (Visit date – Date of birth) / 365.25
- Age (years) at first diagnosis= (Date of first diagnosis – Date of birth) / 365.25
- Age (years) at the initiation of axitinib= (start date of axitinib – Date of birth) / 365.25
- Number of metastatic locations = sum (Lymph nodes, CNS, Hepatic, Pulmonary, Bone, Other).
- • Neutrophil / lymphocyte ratio. It will be categorized as follows:  $\leq 3$ ,  $> 3$ . "Before the beginning of the first line" and "At the beginning of treatment with axitinib" will be analyzed. This ratio is not calculated on axitinib suspension because there is no current lymphocyte value data in that part of the CRF.
- Time (months) between first diagnosis and nephrectomy = (Date of nephrectomy – Date of first diagnosis) / 30.4375. A list with the information (site, patient, date of first diagnosis, date of nephrectomy and the calculated time) in cases in which the time is negative (with date of nephrectomy before or equal to date of first diagnosis) will be displayed, and these cases will not be included in the descriptive analysis
- Time (months) between first diagnosis and radiotherapy = (Date of radiotherapy – Date of first diagnosis) / 30.4375. A list with the information (site, patient, date of first diagnosis, date of radiotherapy and the calculated time) in cases in which the time is negative (with date of radiotherapy before or equal to date of first diagnosis) will be displayed, and these cases will not be included in the descriptive analysis.
- Time (months) between first diagnosis and 1st-line treatment = (Date of the initiation of 1st-line treatment – Date of first diagnosis) / 30.4375. A list with the information (site, patient, date of first diagnosis, date of 1st-line treatment and the calculated time) in cases in which the time is negative (with date of 1st-line treatment before or equal to date of first diagnosis) will be displayed, and these cases will not be included in the descriptive analysis

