- Duration of first-line treatment:([0-3] months, [3-6] months, [6-9] months, [9-12] months,  $\geq 12$  months).
- Duration of first-line treatment: ( $\leq 9$ months,  $>9$  months).
- Duration of first-line treatment: ( $\leq 12$ months,  $>12$  months).
- Duration of first-line TKi treatment: ([0-3] months, [3-6] months, [6-9] months, [9-12] months,  $\geq 12$  months).

It will be calculated the duration of the first line, if the drug was only a TKi.

- Duration of first-line TKi treatment: ( $\leq 9$ months,  $>9$  months).
- Duration of first-line TKi treatment: ( $\leq 12$ months,  $>12$  months).
- Duration of the first TKI treatment:( [0-3] months, [3-6] months, [6-9] months, [9-12] months,  $\geq 12$  months).

It will be calculated the duration of the first treatment with a TKi, in 1st or later line (always after axitinib).

- Patients treated with a TKi previous to axitinib other than first. It will be analysed the number of patients with a TKi previous to axitinib, different from the first TKi received.

It will be analysed the duration of this treatment.

- Best response with the TKI received in the first-line (CR, PR, SD, DP)
- Best response with a TKi previous to axitinib with a TKi other than first line (CR, PR, SD, PD).
- Best response with line prior to axitinib with a TKI if a line prior to axitinib other than the first one has been received (CR/PR, SD, DP).
- Number of metastatic locations (1, 2 and  $\geq 3$ ); See this definition in section 7 Definitions of variables and objectives.
- Site of metastases (CNS metastases [yes vs no]; lymph nodes [yes vs no]; lung [yes vs no]; liver [yes vs no]; bone [yes vs no]). In addition to showing the descriptive and comparative table of metastatic locations between groups, another similar table will be shown but with the categories “Hepatic” and “Bone” united in a single.
- Neutrophil/lymphocyte ratio  $\leq 3$  (yes vs no). See this definition in section 7 Definitions of variables and objectives. It will be analysed in all moments included in the study.
- Line of treatment in which it was received.

- 
- Presence of comorbidities.
  - Suspension of treatment.
  - Have you received any further treatment?
  - Has there been disease progression?
  - Best response to treatment (RC, RP, EE, PE).
  - Best response to treatment (RC / RP, EE, PE).
  - Duration of axitinib treatment.
  - Vital status

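### The neutrophil/lymphocyte ratio can be calculated as a number, but the SAP analyses it only as ≤3 versus >3, which loses at least about 36% of its information if the effect is linear on the log scale

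*SAP*

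**What the plan says.** **Collection (SAP 6).** Before first line the CRF has "Neutrophils > ULN (Yes/No/Unknown)- (current value)" and "Lymphocytes (Yes/No/Unknown)- (value)". At axitinib start it has "Neutrophils > ULN (Yes/No/Unknown) (value)" and "Lymphocytes (Yes/No/Unknown) (value)". The other laboratory risk criteria have no value field. LDH, for example, is "LDH >1.5 x ULN (Yes/No/Unknown)", and haemoglobin, corrected calcium and platelets follow the same pattern.

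**Derivation (SAP 7).** The entry reads "Neutrophil / lymphocyte ratio. It will be categorized as follows", followed by ≤3 and >3, at two times: before first line and at axitinib start. It is not derived at axitinib discontinuation because no lymphocyte value is recorded there. The SAP therefore treats the value fields as usable at the other two times.

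**Analysis (SAP 7.1).** The factor list gives the ratio as ≤3, yes versus no, and adds: "See this definition in section 7 Definitions of variables and objectives. It will be analysed in all moments included in the study". Baseline factors studied in this way go to the logistic model if P<0.05 or P<0.15, and the final model keeps those with P<0.05. Number of previous lines and duration of first-line treatment are each listed both uncategorised and in categories.

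**Protocol 7.1.** "Neutrophil/lymphocyte ratio" ≤3, yes versus no, is one of the factors whose association with benefit is to be analysed under the primary objective.

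**The concern.** A two-class coding treats ratios of 2.9 and 3.1 as different, and ratios of 3.1 and 12 as the same. If the chance of being a long responder rather than refractory changes gradually with the ratio, part of the signal is removed before any test is run.

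The study expects about 60 patients, and identifying associated factors is its primary objective. A marker with a real association can fail the P<0.15 screen, or drop out of the final model, because of how it was coded. For LDH, haemoglobin, calcium and platelets that detail was never collected. For the ratio it was collected and is then not used.

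**Working it through.** The plan states no power, effect size or calculated sample size, so there is no figure of its own to reproduce.

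**Inputs from the documents**
- Expected number of patients: about 60 (Protocol 8.5; SAP 2.1, Sample size).
- Long responders to refractory patients: about 2:1 (Protocol abstract, study population), so about 40 and 20.
- Two-sided α = 0.05 (SAP 4 and 9.1).

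**Assumptions, not in the documents**
- Log ratio is normal with equal SD in the two groups, and its effect is linear.
- Share of patients above 3, called p: varied from 10% to 50%.
- The ratio is known for all 60 patients.

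**Step 1. Information kept by the split.** With c the standard normal point that leaves a share p above it, and φ the normal density:

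efficiency = φ(c)² / [p(1 − p)]; loss = 1 − efficiency.

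At p = 0.5, c = 0 and φ(0)² = 1/(2π), so efficiency = [1/(2π)]/0.25 = 2/π = 0.637.

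| Share above 3 | Efficiency | Loss | Equivalent of 60 patients |
|---|---|---|---|
| 50% | 0.637 | 36% | 60 × 0.637 = 38.2 |
| 40% | 0.622 | 38% | 37.3 |
| 30% | 0.576 | 42% | 34.5 |
| 20% | 0.490 | 51% | 29.4 |
| 10% | 0.342 | 66% | 20.5 |

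The formula is symmetric in p and 1 − p. The loss is smallest at an even split, so 36% is the minimum under this model.

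**Step 2. What this does to power at 40:20.** Take a between-group difference of 0.767 SD in log ratio, chosen because it gives the continuous analysis 80% power. The standard error is √(1/20 + 1/40) = 0.274 SD, 0.767/0.274 = 2.80, and 2.80 − 1.96 = 0.84, which corresponds to 80%. The cut is then placed so that a share p of all patients lies above it, and the two proportions are compared.

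| Share above 3 overall | Above 3: long responders / refractory | Power, two proportions |
|---|---|---|
| 50% | 0.401 / 0.697 | 58% |
| 40% | 0.301 / 0.597 | 60% |
| 30% | 0.209 / 0.483 | 58% |
| 20% | 0.125 / 0.350 | 54% |
| 10% | 0.052 / 0.196 | 43% |

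A simulation of 20,000 studies per setting agrees. The t test on the continuous value has 79% power. At 50%, 30% and 20% above 3, the chi-squared test has 61%, 59% and 53%, and Fisher's exact test has 50%, 54% and 46%.

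**The case against.** **The cut at 3 was pre-specified.** It stands in Protocol 7.1 (version of 21 March 2018), so it was not picked from the data. That is right and should be credited, but it answers cut-point selection, not information loss. A reader might also infer that the cut-off has no basis. The documents do not allow that conclusion, because the study rationale in Protocol 6.2 ends in redacted text.

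**A late change is itself post hoc.** SAP section 1 records that version 3 followed a draft of results. Replacing the ≤3 form now would depart from Protocol 7.1, and Protocol 8.7 requires major changes to the primary analyses to be reflected in a protocol amendment. This stands. It rules out replacement, but not a labelled addition.

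**Categorised factors are the SAP's general style.** Age is calculated in years but listed in 7.1 only as ≤65 versus >65, and the count of metastatic sites only as 1, 2 and ≥3. The ratio is therefore not an anomaly. Still, the SAP does list two factors in both forms. For first-line TKI duration, Protocol 7.1 gives categories only, whereas the SAP adds an uncategorised first-line duration.

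**The study is exploratory, and uncovered CRF variables will be described (SAP 9.2, Other analyses).** That may show the raw counts, but it gives neither the continuous ratio nor its place in the model.

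**A reader might infer that the ratio is the only laboratory marker recorded as a number.** It is not recorded at all; it is derived. Neutrophils have their own value field and are separately analysed as above ULN, yes or no.

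**A reader might add residual confounding.** SAP 7.1 builds a prognostic-factor model and estimates no exposure effect, so that charge does not fit.

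**Conclusion.** The point holds as a minor improvement. The ratio can be calculated as a number at two times, is specified only as ≤3 versus >3, and can enter the screen and model only in that form.

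If log ratio is roughly normal with a linear effect, the loss is at least about 36%. It is about 42%, 51% and 66% if 30%, 20% and 10% of patients exceed 3.

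A reader might take a range such as 36–42% as a property of this study. The documents do not support that: they give no distribution of the ratio, and the range needs roughly 30–70% of patients above 3. If the true effect were a step at 3, the loss would not apply. The patient equivalents also assume complete data, whereas the lymphocyte item has an Unknown option and SAP 8 imputes nothing except incomplete dates.

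**What to change.** In SAP 7 and 7.1, add the ratio at axitinib start as a continuous variable on the log2 scale:
- in the comparison of long responders with refractory patients, using the tests for continuous variables already in SAP 9.1;
- as a candidate for the logistic model, reported as an odds ratio per doubling.

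Keep ≤3 versus >3 in the association analysis, since Protocol 7.1 specifies it there. Report both forms whatever they show, and label the continuous one as added after the draft of results. Because both forms carry the same marker, fit them in separate models and do not choose between them by P value.

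The cost is SAP wording and one extra analysis, with no new data. It also adds one more test in a plan without multiplicity adjustment, and an odds ratio per doubling is less familiar to clinicians than a cut-off.

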- Duration (months) of previous 1st-line treatment = (Date of end of 1st-line treatment – Date of start of 1st-line treatment) / 30.4375. If a patient is detected in whom this duration cannot be calculated or a negative time is left, it will not be considered in the descriptive analysis, and a list will be shown with the information related to this calculation of said patient.

- 
- Pre-treatment of 1st line: a descriptive table with the collected drugs will be shown (if necessary, a list will be sent to the sponsor for the grouping of these drugs). In addition, the registered drugs will be grouped into three groups: Sunitinib, Other iTK, and Others, and the descriptive table will be included in the report.
  - Duration (months) of previous 2nd-line treatment =  
 $(\text{Date of end of 2nd-line treatment} - \text{Date of start of 2nd-line treatment}) / 30.4375$ . If a patient is detected in whom this duration cannot be calculated or a negative time is left, it will not be considered in the descriptive analysis, and a list will be shown with the information related to this calculation of said patient.
  - Duration (months) of previous 3rd-line treatment =  
 $(\text{Date of end of 3rd-line treatment} - \text{Date of start of 3rd-line treatment}) / 30.4375$ . If a patient is detected in whom this duration cannot be calculated or a negative time is left, it will not be considered in the descriptive analysis, and a list will be shown with the information related to this calculation of said patient.
  - Duration (months) of previous 4th-line treatment =  
 $(\text{Date of end of 4th-line treatment} - \text{Date of start of 4th-line treatment}) / 30.4375$ . If a patient is detected in whom this duration cannot be calculated or a negative time is left, it will not be considered in the descriptive analysis, and a list will be shown with the information related to this calculation of said patient.
  - Duration (months) of previous 5th-line treatment or further =  $(\text{Date of end of 5th-line treatment} - \text{Date of start of 5th-line treatment}) / 30.4375$ . It will be analyzed only if there is an adequate sample (enough high) of patients with 5th or later previous lines.
  - Duration (months) of treatment with axitinib =  
 $(\text{Date of end of axitinib treatment or of latest follow-up if not suspended} - \text{Date of start of axitinib treatment}) / 30.4375$
  - Time (months) to increase or Time (months) to reduction of axitinib dose =  

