## **8 MANAGEMENT OF MISSING DATA**

In the event of incomplete dates, proceed as follows:

- If the year XXXX is known, but not the day or month, 15/06/XXXX will be entered.
- If the month YY and year XXXX are known, but not the day, 15/YY/XXXX will be entered.

For all other variables, no criterion for substituting missing data will be used.

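### Same-day intervals from first diagnosis are classed as negative and dropped, so the mean times to nephrectomy, radiotherapy and first-line start are overstated whenever such ties occur

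*SAP*

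**What the plan says.** SAP section 7 (Definition of variables and objectives) computes each interval as a date difference in months. For nephrectomy the formula is "Date of nephrectomy – Date of first diagnosis) / 30.4375".

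Each of the three intervals has an exclusion rule:

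- Nephrectomy: a listing is produced "in cases in which the time is negative (with date of nephrectomy before or equal to date of first diagnosis) will be displayed".
- Radiotherapy: a listing is produced "in cases in which the time is negative (with date of radiotherapy before or equal to date of first diagnosis) will be displayed".
- First-line start: the same form, ending "line treatment before or equal to date of first diagnosis) will be displayed".

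All three add "and these cases will not be included in the descriptive analysis". The listing shows site, patient, both dates and the calculated time.

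For the durations of previous lines 1 to 4, section 7 uses a different condition: when "this duration cannot be calculated or a negative time is left, it will not be considered in the descriptive analysis". A duration of zero passes that test.

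SAP section 8 (Management of missing data) fills in partial dates: "If the month YY and year XXXX are known, but not the day, 15/YY/XXXX will be entered". When only the year is known, the date becomes 15 June of that year.

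**The concern.** Each of the three rules contradicts itself. It names negative times, but its bracket also takes in equality, and equal dates give exactly zero. Zero is a legitimate value: a tumour can be diagnosed on the nephrectomy specimen, so that diagnosis and surgery share a date. The section gives no reason for excluding zeros here while keeping them for treatment durations.

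Ties can also come from the plan itself. Two dates in the same month with unknown days both become the 15th, and two year-only dates in the same year both become 15 June. The SAP provides for incomplete dates, so it expects some in this chart review.

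The rule removes values only from the lower end of a non-negative distribution, so the error runs in one direction. At stake is the accuracy of three baseline summaries. They might also feed the comparison of baseline clinical history between long-term responders and refractory patients in SAP section 9.2.

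**Working it through.** The plan states no figure for these intervals, so there is none to reproduce.

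**Inputs from the SAP.** The divisor of 30.4375, the three exclusion rules and the duration rule (section 7); the imputation rule (section 8); about 60 patients expected (section 2.1, Sample size).

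**Assumed input.** p0, the share of valid (zero or positive) intervals that equal zero. The documents do not give it; the range used is 2% to 30%.

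**Step 1, a same-day pair.** 0 / 30.4375 = 0. This is not negative, but it meets the bracketed condition and is excluded.

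**Step 2, the mean.** Zeros add nothing to the sum, so the mean of all valid intervals is (1 − p0) × the mean of the positive ones. The SAP rule reports the mean of the positive ones, which is too high by the factor 1/(1 − p0).

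**Step 3, the median.** The median of the positive intervals lies at quantile p0 + 0.5(1 − p0) of all valid intervals.

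| Assumed p0 | Zeros among 60 | Mean too high by factor | Reported median is this percentile of valid intervals |
|---|---|---|---|
| 2% | about 1 | 1.02 | 51 |
| 5% | 3 | 1.05 | 52.5 |
| 10% | 6 | 1.11 | 55 |
| 20% | 12 | 1.25 | 60 |
| 30% | 18 | 1.43 | 65 |

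The second column assumes that all 60 patients have the interval. Fewer will for radiotherapy, and perhaps for nephrectomy.

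**Step 4, in months (illustration only).** Suppose positive intervals are exponential with mean m and p0 = 20%. The median of all valid intervals is −m ln(1 − q), with q = (0.5 − 0.2)/0.8 = 0.375; the median after exclusion is m ln 2.

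- m = 1.5: the mean goes from 1.20 to 1.50 months and the median from 0.71 to 1.04.
- m = 12: the mean goes from 9.6 to 12 months and the median from 5.64 to 8.32.

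The proportional change is the same in both cases. The shift in months scales with m, and the documents give no value for m.

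**Step 5, ties made by imputation.** Suppose both days are missing, the diagnosis date is uniform over a month and the true interval is exponential. The chance that both dates fall in one month, and so become a tie, is 1 − m(1 − e^(−1/m)).

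- m = 1.5: 1 − 1.5 × (1 − 0.513) = 0.27.
- m = 3: 1 − 3 × (1 − 0.717) = 0.15.

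These are shares of pairs with both days missing, not of all patients, and they fall as m grows.

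**The case against.** The strongest reply is that little depends on these intervals and that the plan already shows what it leaves out. Much of this stands.

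- **Visibility.** Every excluded case is listed with its dates, so a reader of the report could find a same-day case and restore it. The patient stays in the full analysis set and in the yes/no nephrectomy factor. But the case would be listed under the label of a negative time, and the summary would still omit it.
- **Reach.** The intervals are not in the protocol's objectives, the factor list in SAP 7.1 or the table list in SAP section 10. The only route to inference is the general baseline comparison in SAP 9.2 and the model screening it might feed. The SAP does not say that these intervals take part.
- **Size.** No document gives the number of ties. The specimen-based reason for a zero applies to nephrectomy; for radiotherapy and first-line start, ties are less obvious apart from imputation. An interval mean of 1.5 months is at most plausible for nephrectomy. The SAP's risk scores split time from diagnosis to systemic treatment at one year, so first-line intervals may be much longer.

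A reader might infer that the rule distorts the survival results or moves patients between risk groups. The documents do not support this. PFS, TTP and OS from axitinib run from the start of axitinib, and the additional OS runs from the start of first line. The response groups rest on PFS and best response. The under-one-year risk factor is a separate Yes/No/Unknown item in the CRF (SAP section 6). A reader might also infer a known, large bias, but that would need a tie count the documents do not give.

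**Conclusion.** The three rules are wrong as written: they exclude valid zero intervals, against their own word for what is excluded and against the rule for treatment durations in the same section. The direction is certain. With at least one zero and one positive time, the reported mean is too high, and the median cannot fall. The size is unknown: a factor of 1.02 to 1.43 on the mean for an assumed p0 of 2% to 30%, and 1 if there are no ties. This is a minor correction to descriptive summaries, with a possible but unstated link to the baseline group comparison. The factor rests only on p0; the figures in months and the tie probabilities also rest on the exponential assumption and on the chosen means.

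**What to change.** In the three interval rules of SAP section 7, delete the words *or equal to*, so that only an event dated strictly before diagnosis is listed and left out. Keep zeros in the descriptive analysis. Report the number excluded for each interval, and flag every zero in which either date was imputed under section 8, so that the reader can tell recorded ties from artificial ones.

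The cost is small but not nil. SAP version 3 was issued after a draft of the results, so the affected tables must be rerun. An imputed zero that is kept may understate a true interval: by less than a month when two dates share a known month, but by up to most of a year when both are year-only. The change also does not recover every short interval. If the diagnosis day is imputed as the 15th and the event carries a recorded earlier day in that month, the result is strictly negative and is still excluded; the listing should mark these cases too.
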